- **Consortium Agreement**. The agreement concluded amongst PROMISE participants for the implementation of the Grant Agreement. The agreement shall not affect the parties' obligations to the Community and/or to one another arising from the Grant Agreement.

Abbreviations

Acronym / Abbreviation	Meaning
ABR	General Assessment and Registration form (ABR form), the application form that is required for submission to the accredited Ethics Committee; in Dutch: Algemeen Beoordelings- en Registratieformulier (ABR-formulier)
AE	Adverse Event
AR	Adverse Reaction
CA	Competent Authority
CCMO	Central Committee on Research Involving Human Subjects; in Dutch: Centrale Commissie Mensgebonden Onderzoek
CV	Curriculum Vitae
DSMB	Data Safety Monitoring Board
EU	European Union
EudraCT	European drug regulatory affairs Clinical Trials
GCP	Good Clinical Practice
GDPR	General Data Protection Regulation; in Dutch: Algemene Verordening Gegevensbescherming (AVG)
IB	Investigator's Brochure
IC	Informed Consent
IMP	Investigational Medicinal Product
IMPD	Investigational Medicinal Product Dossier
METC	Medical research ethics committee (MREC); in Dutch: medisch-ethische toetsingscommissie (METC)
RSV	Respiratory Syncytial Virus
(S)AE	(Serious) Adverse Event
SPC	Summary of Product Characteristics; in Dutch: officiële productinformatie IB1-tekst
Sponsor	The sponsor is the party that commissions the organisation or performance of the research, for example a pharmaceutical company, academic hospital, scientific organisation or investigator. A party that provides funding for a study but does not commission it is not regarded as the sponsor, but referred to as a subsidising party.
SUSAR	Suspected Unexpected Serious Adverse Reaction
UAVG	Dutch Act on Implementation of the General Data Protection Regulation; in Dutch: Uitvoeringswet AVG
WMO	Medical Research Involving Human Subjects Act; in Dutch: Wet Medisch-wetenschappelijk Onderzoek met Mensen

Abstract/Summary

Rationale: Human respiratory syncytial virus (RSV) causes severe disease in young infants. Besides young age, prematurity and congenital cardiopulmonary disease are known risk factors for severe disease. However, most children admitted to the hospital with RSV are previously healthy. To identify those at risk for severe disease, biomarkers are needed. In the RESCEU case-control study we established biomarkers predictive of, or associated with, lower respiratory tract RSV infection and disease severity. In this follow-up study the detected biomarkers will be validated.

Objective:

To validate biomarkers that are associated with severe RSV infection and respiratory sequelae.

Study design: Prospective observational case-control study

Study population:

Previously healthy infants (<1 year of age) with a proven RSV infection in the following subgroups:

- Ventilated infants (n=40)
- Hospitalized, non-ventilated infants (n=40)
- Medically attended non-hospitalized infants (n=40)
- Healthy infants (n=40)

Main study parameters/endpoints: Validation of biomarkers that are associated with severe RSV infection and respiratory sequelae.

Nature and extent of the burden and risks associated with participation, benefit and group relatedness: Blood, respiratory, buccal, urine and stool samples will be collected at the moment of medical attendance for RSV infection and 6-8 weeks after infection. Healthy controls will have only one timepoint (baseline) at which samples are collected. A questionnaire will be completed by the parents at the moment of RSV infection (baseline) followed by a diary for two weeks (14 consecutive days) for RSV positive children. A yearly questionnaire up to the age of 3 years old will be completed by the parents.

None of the study procedures is associated with any risk for serious complications. However, there is a minimal risk of minor complications due to study procedures (for example a nose bleed after a nose swab or bruise after blood sampling). This study is group related and can only be done in this patient group because severe RSV disease is mainly seen in infants and very rare in older children and adults.

Benefits of participating in the study: There are no particular benefits to participating in this study, apart from knowing that knowledge obtained from it may benefit other patients in the future.

1. Introduction and study design

1.1. Introduction

Human respiratory syncytial virus (RSV) causes severe disease in the very young, elderly and in high risk groups. Worldwide in 2015 there were an estimated 34 million cases of acute lower respiratory tract infection (ALRI), 3.4 million ALRI hospitalisations and 55,000 to 199,000 deaths associated with RSV in children <5 years old (1). Although RSV related mortality is rare in developed countries, the burden of RSV related hospitalization is substantial with an estimated yearly hospitalization rate of 0,8% in infants (2, 3). The majority of children admitted to the hospital with RSV are previously healthy. Although a younger age is a risk factor for severe disease in children without comorbidities, this cannot totally explain the difference in severity between young children of the same age. In addition, RSV infection in infancy is associated with recurrent wheezing episodes in the first year of life and beyond (4, 5). Given this substantial burden, there is an unmet need to identify the correlates of severe RSV disease for clinical management, classification of disease severity in clinical trials and identification of biomarkers for severe disease, which are currently lacking (6).

The RESCEU (Respiratory Syncytial virus Consortium in Europe) consortium, an IMI funded effort which brought together clinicians, epidemiologists, basic scientists, health economists, statisticians, public health professionals and industry from across Europe to answer key research questions relating RSV, conducted a biomarker discovery study in healthy young infants with RSV infection in 2 prospective studies, the RESCEU infant cohort study and the RESCEU infant case-control study (7, 8). First, possible biomarkers were identified by means of a systematic literature review (9). Biomarkers discovered in RESCEU include, but are not limited to: an array of RSV antibodies, including prefusion F protein (preF), postfusion F protein (postF) and neutralizing antibodies; gene expression profiles in infant whole blood at birth (susceptibility) as well as during disease (severity, prognosis). Results are currently being analysed and will be prepared for publication in the coming months.

A critical step in biomarker development is external clinical validation (10) as biomarkers are often identified in data-driven exploratory studies which increase the chance of false positive associations. Therefore, they need to be externally validated to minimise this risk and become acceptable for clinical implementation. This is also part of the regulatory requirements before introduction into routine care. In PROMISE we will establish a clinical study large enough to externally validate the biomarkers identified from RESCEU as well as those that are still being analysed. Gene expression profiles related to neutrophil degranulation as well as innate immunity and antiviral responses will be of specific interest for validation. The most promising candidates will be selected for verification, based on their biological relevance, statistical significance, and potential contribution to a clinical question (if the potential contribution is very small, candidates that did show statistically significance may not be developed further).

1.2. Objectives

Primary Objective:

- To validate biomarkers that are associated with severe RSV infection and respiratory sequelae.

Secondary Objective(s):

- To analyze dynamics of biomarkers in the upper and lower airways of children with RSV infection and compare these with blood
- To validate currently used case definitions and severity measures for RSV infection in infants

- To determine risk factors for severe RSV disease
- To determine long term sequelae of RSV infection in the first year of life

1.3. Study design

This will be a monocenter, prospective, observational case-control study conducted across 2 consecutive years in the Wilhelmina Children's hospital and surrounding general practitioner (GP) offices and general hospitals. This case-control study will validate discovered biomarkers related to RSV infection susceptibility and disease severity in the RESCEU case-control study and birth cohort study. In addition, dynamics of the same biomarkers will be analysed in the upper and lower airways to better understand the sources of these biomarker signals. For this a validation cohort of previously healthy infants with different severities of RSV infection will be used and compared to healthy infants.

The following subgroups will be studied:

- Ventilated infants (n=40)
- Hospitalized, non-ventilated infants (n=40)
- Medically attended non-hospitalized infants (n=40)
- Healthy infants (n=40)

Children will be recruited during two RSV seasons. If RSV is suspected but not tested as part of routine care a point of care test for RSV will be done. Samples will be collected within 96 hours after hospitalization or start of symptoms in infants who are not admitted and repeated after 6-8 weeks (convalescence). Healthy infants will be recruited year round. Collection of samples of healthy controls will be done once. There will be annual follow up by questionnaire for up to 3 years.

Blood, stool, buccal, urine and nasopharyngeal samples will be obtained from all RSV positive infants at moment of infection and in convalescence 6-8 weeks later. In ventilated RSV positive infants, bronchoalveolar lavage (BAL) and/or tracheal aspirate samples will be obtained in combination with routine clinical care. Healthy infants will have blood, stool, buccal, urine and nasopharyngeal samples only at enrolment (i.e. there will be no follow up sampling).

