1.4. Study population

1.4.1. Population (base)

The total study population consists of 160 (previously) healthy infants (<1 year of age). 120 infants with RSV infection will be recruited, who are divided in the following groups:

- Ventilated infants (n=40)
- Hospitalized, non-ventilated infants (n=40)
- Medically attended non-hospitalized infants (n=40)

In addition a group of healthy infants (n=40) without infection at moment of sampling will be recruited to validate whether the discovered biomarkers would also be able to distinguish between infants with and without infection.

All infants will be recruited at the Wilhelmina Children's hospital and surrounding GP offices and general hospitals during 2 consecutive RSV seasons.

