2.2. Study procedures

2.2.1. Main study parameter/endpoint

Participants are recruited at the moment of acute respiratory infection in hospital, at the emergency department, or GP offices.

In hospital setting (inpatient and outpatient department, emergency department):

Potential participants for the study will be identified by clinical research staff. A member of the paediatric clinical research team will identify any potentially eligible participants by attending doctor's handovers, talking to the clinical staff in hospital departments and/or screening hospital computer systems. Potential participants are informed about the study by a member of the clinical team. If parents are interested in participating in the study, a member of the study team will provide verbal and written information about the study. Medical records will be screened to confirm eligibility for inclusion, either after full consent has been received or with verbal permission from the parent/guardian/legally authorised representative. If the potential participant's RSV status cannot be determined from the medical records, written consent will be sought to perform a bedside test to assess for eligibility.

In community setting (general practitioners office):

Potential participants for the study will be identified by the general practitioner during consultations. Potentially eligible and interested participants are referred to the clinical research staff by the general practitioner. A member of the research team will contact the parents/legal guardians of potentially candidates and will explain the study. If they are expressing an interest, written consent will be sought to perform an RSV point of care test to assess for eligibility.

Healthy control infants will be identified in hospital. Patients who are in hospital for minimal invasive elective surgery procedures which are not considered to have an effect on the general health of the infant (for example correction of inguinal herniation, orchidopexy, correction of polydactyly etc) or regular check-up which requires the drawing of blood are identified by attending doctor's handovers, talking to the clinical staff in hospital departments or screening hospital computer systems. Potential

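### Section 1.3 promises to validate RSV susceptibility biomarkers, but no RSV case is sampled before infection and the controls are not tested for RSV afterwards

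*Protocol*

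**What the plan says.** Section 1.3 of the protocol sets two validation targets in one sentence: "This case-control study will validate discovered biomarkers related to RSV infection susceptibility and disease severity in the RESCEU case-control study and birth cohort study".

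Section 1.1 separates these targets by sampling time. Among the discovery findings it lists "gene expression profiles in infant whole blood at birth (susceptibility) as well as during disease (severity, prognosis". The susceptibility profile was thus read at birth, and the severity and prognosis profiles during illness.

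The sampling schedule for this study is as follows.
- **RSV cases (3 × 40 = 120).** Section 2.2.1: "Participants are recruited at the moment of acute respiratory infection in hospital, at the emergency department, or GP offices". Section 1.3: "samples will be obtained from all RSV positive infants at moment of infection and in convalescence 6-8 weeks later". The time limit for the first sample is given as "Samples will be collected within 96 hours after hospitalization or start of symptoms in infants who are not admitted and repeated after 6-8 weeks (convalescence".
- **Controls (40 healthy infants).** Section 1.3: "Healthy infants will have blood, stool, buccal, urine and nasopharyngeal samples only at enrolment (i.e. there will be no follow up sampling". Section 1.4.1 gives their purpose: "to validate whether the discovered biomarkers would also be able to distinguish between infants with and without infection".

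After enrolment, section 2.2.1 gives healthy infants one contact about illness at one week. Parents then complete yearly questionnaires on respiratory symptoms up to age 3. No RSV test is described at any of these contacts.

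The objectives (section 1.2) and endpoints (section 2.1) cover severe disease, sequelae, airway-versus-blood dynamics, case definitions and risk factors for severe disease. None names susceptibility to infection. Section 4.1 adds that an infant recruited as non-hospitalised and later admitted is moved to the hospitalised or ventilated group.

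**The concern.** To validate a susceptibility marker, the marker has to be measured before infection and infection has to be ascertained afterwards. Neither group of infants provides both. The gene-expression profiles that section 1.1 singles out for validation concern neutrophil, innate-immune and antiviral activity, which infection can itself change. A difference between infected and healthy infants in such a profile, or in antibody, could be an effect of the infection.

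Section 1.1 presents the study as external validation on the way to clinical use and regulatory acceptance. Section 4.2, item 3, also plans comparisons of severity groups with healthy controls that include laboratory results. With section 1.3 as it stands, a positive contrast could be reported as validated susceptibility when the data show only that infected infants differ from uninfected ones.

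There is a smaller, related matter of timing within the severity comparison. Under the regrouping rule in section 4.1, the hospitalised and ventilated groups can contain some samples taken before the infant reached that level of care and others taken after. The protocol describes no marker of which is which.

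**Working it through.** The point turns on when samples are taken, and the protocol has no figure to reproduce beyond the group sums: 3 × 40 = 120 cases and 4 × 40 = 160 infants.

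**Step 1. Set the required timing against the planned timing.**

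| | Sample before RSV infection | RSV ascertained afterwards | Can test susceptibility in blood |
|---|---|---|---|
| Discovery profile (section 1.1) | at birth | not described here | taken as given |
| RSV cases, n = 120 | none: acute phase and 6-8 weeks later | already infected | no |
| Healthy infants, n = 40 | one sample, uninfected at the time | no RSV test planned | no |

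The count of cases with a birth or pre-infection sample is 0 of 120. The convalescent sample also follows the infection and cannot stand in for a birth sample. No link to stored birth or cord blood is described.

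**Step 2. Could the healthy infants' samples be reused as pre-infection samples?** Section 1.1 gives a yearly RSV hospitalisation rate of 0.8% in infants. Assume that all 40 are followed for a full further year at that rate and that admissions are independent.
- Expected admissions: 40 × 0.008 = 0.32.
- P(none) = (1 − 0.008)^40 = 0.725, about 73%.
- P(at least one) = 1 − 0.725 = 0.275, about 27%.
- P(at least two) = 0.041, about 4%.

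A full year is generous, since controls may already be several months old at sampling. Milder RSV infections would be more common, but the planned questionnaires would not confirm them. To observe 40 hospitalised cases prospectively at this rate would need 40 / 0.008 = 5,000 infants. The healthy group therefore cannot fill the gap.

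**Step 3. Which measures escape the problem?** Germline DNA does not change with infection. The buccal swab (Table 1, DNA/GWAS) could in principle support a comparison of inherited markers.

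**Step 4. Timing relative to the outcomes in the primary objective.**
- *Acute severity.* An infant already ventilated when sampled has reached the outcome, so that sample shows association. An infant sampled before escalation gives information on prediction, with infants who did not escalate as comparators. The protocol gives no number of infants expected to be regrouped.
- *Sequelae.* These are assessed at ages 1, 2 and 3 years. For sequelae that arise after the acute episode, the acute sample comes first in every RSV group.

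**The case against.** The strongest reply is that *susceptibility* appears as a validation target in one descriptive sentence, and that no objective, endpoint or planned analysis depends on it. The primary objective speaks of association, which a case-control design can support, and section 1.4.1 describes the healthy-infant contrast openly as one of current infection. This stands, and it limits the point to a claim that the design does not support. It does not remove the point, because the sampling schedule is fixed in the protocol and a statistical analysis plan cannot supply the missing samples.

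Four stronger readings are tempting, and the documents do not support them.
- *No infant at all is sampled before infection.* The 40 healthy infants are uninfected when sampled. What they lack is RSV ascertainment afterwards. The supported count is 0 of 120 cases.
- *The study cannot say anything predictive.* Sequelae are part of the primary objective and come after the acute sample. Restating the aim as concurrent severity alone would wrongly drop them.
- *The summary claims to predict risk.* The line "To identify those at risk for severe disease, biomarkers are needed" is background on need and is not a claim about this study.
- *Susceptibility cannot be tested in any form.* The list of discovered markers in section 1.1 is expressly open-ended, its antibody markers carry no sampling time, and germline DNA is collected. What cannot be validated is the one marker that the protocol labels as susceptibility.

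It can also be said that regrouping by the severity reached is reasonable, that it is a separate matter from susceptibility, and that a timing flag or sensitivity analysis is often left to the analysis plan. The regrouping rule itself is not faulted here. The flag is proposed because the same change of wording should settle what may be called predictive, and because sample timing is easiest to record at collection.

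**Conclusion.** The point holds in a limited form. Section 1.3 claims a validation of susceptibility that the sampling cannot deliver: 0 of 120 RSV cases have a pre-infection sample, and the 40 controls have one uninfected sample with no RSV testing to follow. A blood RNA or antibody difference between cases and controls would show that the marker distinguishes current or recent infection. It would not show that the marker preceded infection.

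The primary objective, association with acute severity and with later sequelae, remains testable. The effect of regrouping on the severity comparison is unknown, since the number of infants concerned is not given.

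The conclusion rests on the protocol as shown, which describes no link to birth samples and no RSV testing of controls after enrolment. The 0.32 expected admissions is a side check that assumes a full year at risk at 0.8% and counts hospitalised cases only.

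**What to change.** 1. In section 1.3, do one of three things: delete *susceptibility*; limit it to markers unaffected by infection, meaning germline DNA from the buccal swab; or name a source of pre-infection samples together with the way in which later RSV infection will be ascertained.
2. State there that the study validates association with acute RSV severity and with later respiratory sequelae, and that the healthy-control contrast concerns current infection only.
3. In section 4.1, flag each acute sample as taken before or after the infant reached the highest care level. Repeat the severity comparison without infants whose group changed after sampling.
4. For acute severity, use *predictive* only for analyses of samples taken before escalation, with non-escalating infants as comparators. This limit does not apply to later sequelae.

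With either of the first two options in item 1, the cost is a narrower stated scope, one derived variable and one sensitivity analysis. Naming a source of pre-infection samples would cost more; as the working shows, new prospective collection would be a far larger study.

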1.4. Study population

1.4.1. Population (base)

The total study population consists of 160 (previously) healthy infants (<1 year of age). 120 infants with RSV infection will be recruited, who are divided in the following groups:

- Ventilated infants (n=40)
- Hospitalized, non-ventilated infants (n=40)
- Medically attended non-hospitalized infants (n=40)

In addition a group of healthy infants (n=40) without infection at moment of sampling will be recruited to validate whether the discovered biomarkers would also be able to distinguish between infants with and without infection.

All infants will be recruited at the Wilhelmina Children's hospital and surrounding GP offices and general hospitals during 2 consecutive RSV seasons.

1.4.2. Inclusion criteria

In order to be eligible to participate in this study, a subject must meet all of the following criteria:

- Parents/legal guardians of infant are willing and able to give informed consent for participation in the study.
- Less than 12 months of age at enrolment.
- Hospitalized with (suspected) RSV infection for <96 hours at enrolment or within 96hrs of onset of illness (for those not admitted).*

* Not applicable for healthy control infants

